APPENDIX 2: Glossary of terms

Term / acronym	Meaning			
A/B otic	Antipyrine / benzocaine ear drops (the generic term for the CEDAR trial IMP)			
AE	Adverse Event			
AOM	Acute otitis media. For CEDAR, we will use a pragmatic clinical definition of			
	AOM, similar to that used in UK primary care and previous studies , as follows:			
	acute (≤4 days) [Singh 2006] ear pain plus otoscopic evidence of acute			
	inflammation of the ear drum (erythema with dullness or cloudiness or bulging)			
	as confirmed by the child's NHS clinician.			
Auralgan (© or ™)	The brand name under which the CEDAR trial IMP is manufactured and			
	marketed as a pharmacy medicine in Australia and New Zealand by Pfizer			
	Consumer Healthcare.			
BRTC	Bristol Randomised Trials Collaboration			
CED	Children's Emergency Department			
Centre	One of the three universities (Bristol, Cardiff and Southampton), each with a			
	PI, from which Sites will be recruited and co-ordinated.			
CHU-9D	Child Health Utility 9D quality of life questionnaire			
CI	Chief Investigator			
CIS	Child Information Sheet, which is given to any child who is old enough to			
	understand what is being asked of them within the study. The CIS will have			
	been ethically approved.			
Code-break	Record held by UHBristol of allocation of active vs. placebo solution (and			
	Medicine ID number) to Patient ID number.			
CRF	Case Report Form			
Day 1	The day on which the child is consented and entered into either the CEDAR			
	RCT or the OCS			
Day 8	The data collection point representing 7 days after the day of study entry			
DMC	Data Monitoring Committee			
DSUR	Development Safety Update Report			
GCP	Good Clinical Practice			
Illness resolution	The point at which the child's ear pain has been resolved for two consecutive			
	days without the use of medication			
IMP	Investigational Medicinal Product, also referred to as the "Trial Medicine".			
	This is either active ear drops or placebo ear drops.			
Index consultation	The routine consultation with the GCP-trained primary care clinician			
	responsible for the child's routine care.			
Medicine ID number	The unique number assigned to the IMP at manufacture (by the IMP			
	manufacturer using the randomisation data provided by BRTC) and assigned,			
	with the Patient Pack, to the Patient ID number according to the			
	randomisation schedule provided to UH Bristol Pharmacy by the BRTC.			
Medicine pack	The packaging containing the IMP uniquely identified by the Medicine ID			
	number.			
NHS	National Health Service			
NICE	National Institute for Health and Clinical Excellence			
NISCHR	National Institute for Social Care and Health Research (Wales)			
OCS	Observational Cohort Study			
OME	Otitis Media with Effusion			
OMQ-14	Otitis Media Questionnaire: a functional health status measure which best			
	predicts QoL in children with otitis media			
ООН	Out Of Hours clinic			
ОТС	Over The Counter			

APPENDIX 2: Glossary of terms

Term / acronym	Meaning
Patient ID number	The unique number already allocated to the PP which is assigned to the
	recruited child by the Clinician following informed written consent.
Patient pack (PP)	The pack containing all the materials necessary for recruitment. All items will
	be labelled with the Patient ID Number and will include the Medicine ID
	number (which will determine the trial arm to which the participating child is
	allocated), Parent and Child Information, a copy of the Symptom and Recovery
	Questionnaire and pen, and a thank-you voucher.
PI	Principal Investigator
PIS	The ethically approved Parent Information Sheet, which is given to the parent
	of the potentially eligible child on arrival at the primary care site, or by the
	child's Clinician, and also included in the patient pack. All parents will be
	provided with a PIS.
QoL	Quality of Life
Randomisation data	A list of random numbers generated by BRTC in line with the requirements of
	the trial sponsor and of the medicine supplier for their use in numbering the
	medicine packs and patient packs which are provided to UH Bristol Pharmacy.
Randomisation schedule	Instructions provided by BRTC to UH Bristol Pharmacy regarding active vs.
	placebo medicine allocation to Patient Packs.
RCT	Randomised Controlled Trial
Responsible Clinician	The GCP-trained primary care clinician who takes responsibility for the clinical
	management of the child at presentation, confirms the child's eligibility to
	take part in the trial, conducts the clinical examination, signs the trial
	prescription, consents the child / parent and explains to the parent how to
	administer the ear drops.
SAE	Serious Adverse Event
(S)AR	(Serious) Adverse Reaction
Screening ID	The unique number assigned to the child prior to confirming patient eligibility
	for recruitment into the trial during the index consultation. This number will
	be entered onto the trial screening log to allow for tracking of ineligible
	children.
Site	Recruiting primary care site, e.g. GP practice, Children's Emergency
	Department, Out Of Hours clinic or Walk-In Centre
SLA	Service Level Agreement
SOS	Severity of Symptoms
Source data	For the CEDAR trial, the source data will be defined as follows:
	Case Report Forms: the source data will be the electronic data entered by
	clinicians into REDCap at the GP site within 24 hours of recruitment, either
	entered directly online or transcribed at the site from the paper forms.
	Parent Symptom and Recovery Questionnaire: the source data for parents
	completing the diary online will be the electronic data they enter that is
	uploaded into REDCap. For parents completing paper symptom diaries, the
	source data will be considered to be the data recorded on the paper diary IF
	this is more complete than the shadow diary data collected by the trial research
	team in the follow-up telephone calls. For parents whose paper diaries are not
	returned, or where the data returned in the paper diary are less complete than
	the shadow data, the shadow data collected on the phone will be considered as
	the source data.
	Review of primary care medical notes: the source data will be considered to be
	the electronic data entered onto REDCap at the GP practice.
SUSAR	Suspected Unexpected Serious Adverse Reaction

APPENDIX 2: Glossary of terms

Term / acronym	Meaning			
TGA	Therapeutic Goods Administration. The TGA is the arm of the Australian			
	Government Department of Health responsible for regulating therapeutic			
	goods including prescription medicines, vaccines, sunscreens, vitamins and			
	minerals, medical devices, blood and blood products. Almost any product for			
	which therapeutic claims are made must be entered in the Australian Register			
	of Therapeutic Goods (ARTG) before it can be supplied in Australia.			
Trial Participation Card	Parents of children participating in the trial will be requested to carry this with			
	them while the child is participating in the trial. It will record the Medicine and			
	Patient ID numbers to be used for emergency unblinding.			
Trial Prescription				
	The Medicines for Human Use (Clinical Trials) Regulations 2004 (Statutory Instrument 2004/1031 Schedule 1, part 2 [7]) requires that:			
	'The medical care given to, and medical decisions made on behalf of subjects shall always be			
	the responsibility of an appropriately qualified doctor or, when appropriate, of a qualified			
	dentist' The eligibility of a child to take part in the CEDAR trial must therefore be confirmed by a			
	qualified GP.			
	If the child is eligible to participate in the trial (following completion of the			
	If the child is eligible to participate in the trial (following completion of the detailed eligibility check) the Responsible Clinician will authorise a trial			
	prescription. This document is not intended for use by the parent or by any			
	pharmacist and should be kept with the recruitment paperwork pertaining to			
	the child. The purpose of the trial prescription is to confirm the issue of the trial			
	medicine, to document the details of the medicine packs issued to the child,			
	and to record any eligibility decisions made by the Responsible Clinician using			
	his/her clinical judgement. The trial prescription will be completed as part of			
	the recruitment process for children recruited to one of the two active arms of			
	the RCT.			
TSC	Trial Steering Committee			
VAS	Visual Analogue Scale			
WIC	(NHS) Walk-In Centre			

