Parents who decline participation or whose children are ineligible for the trial will be invited to take part in an observational study. In all cases trial participation will be invited prior to extending any invitation to take part in the OCS. This is in order to prioritise entry into the RCT. Participation in the RCT would not involve any change in their management, but would involve collecting data about their presentation, management and follow-up. If parents decline participation in the observational study then they will not be entered into the study but we will record anonymous data in a screening log.

Entry into the RCT or OCS

Entry into the RCT or OCS will be signified by the completion of a valid consent form. Parents agreeing to take part in the RCT will be asked to sign a consent form after which the Responsible Clinician will sign the Trial Prescription

and the parent will be given the Patient Pack and, if the child is allocated to one of the two treatment arms of the RCT, the trial medicines. For parents or carers agreeing to take part in the OCS, the parent will be asked to sign a consent form, either while with the Responsible Clinician, or soon after the consultation and before leaving the site. Any patient subsequently found ineligible or declining to participate will be recorded on a screening form with brief reasons for ineligibility or declining, the remaining data destroyed and a protocol deviation recorded.

Online data collection means instant notification of recruitment to the lead Centre (Bristol). For all patients, including patients recruited using paper forms, GP sites will be asked to fax to the Bristol trial centre by the end of the same working day, evidence of valid consent and the parent's contact details. This will trigger a telephone call to the parent (usually on the same or following day) from the CEDAR trial nurse to address any questions or concerns about the trial or trial medicines.

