- 5) All ANPs participating in the trial will be appropriately qualified and will be assessing and managing children with AOM as part of their routine responsibilities
- 6) All ANPs participating in the trial will have GCP training and will receive face-to-face training by the study team
- 7) All site staff roles and responsibilities will be documented on the delegation log which will be authorised by a medically qualified, GCP trained doctor.

Availability of GCP-trained GP or other medically qualified doctor:

- 8) For sites at which a GCP-trained GP or other medically qualified doctor is present, the site training and delegation logs will be authorised by this GP/doctor.
- 9) For Nurse-led sites at which a GCP-trained GP or other medically qualified doctor is not normally present, the site training and delegation logs will be authorised by the local CEDAR trial centre PI, acting as the GCP-trained GP.
- 10) Recruitment by ANPs at sites at which a GCP-trained GP or other medically qualified doctor is present will be overseen by this GCP-trained GP or other medically qualified doctor, and this oversight will take the form of GP/doctor authorisation of the completed trial prescriptions within a reasonable timescale following recruitment.
- 11) Recruitment from Nurse-led sites at which a GCP-trained GP or other medically qualified doctor is not normally present will be overseen by the CEDAR Chief Investigator as the medically qualified doctor. This oversight will take the form of authorisation of the completed trial prescriptions by the CEDAR CI (or another delegated GCP-trained GP, if the CI is not available) within a reasonable timescale following recruitment.
- 12) In all situations where a GCP-trained GP or medically qualified doctor is not available at a ANP recruitment site, if the ANP needs exceptional medical advice regarding a borderline eligility decision, the ANP will be able to contact a GCP-trained GP via the trial team through an auditable process which will be described in a SOP.

(i) Eligibility assessment

The eligibility of children to take part in CEDAR must be assessed by:

(a) a GCP-trained GP or other medically qualified doctor who has been trained in the trial procedures, OR;

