- (b) a suitably qualified and GCP-trained Nurse or other healthcare professional, who has been trained in the trial procedures, and with oversight from a GCP-trained GP or other medically qualified doctor (oversight in this instance is confirmation that the eligibility decision is correct, established by means of the GCP-trained doctor's signature on the trial prescription prior to the issue of the trial medication), OR
- (c) A suitably qualified and GCP-trained Advanced Nurse Prescriber/Practitioner who has been trained in the trial procedures, with oversight from a GCP-trained GP or other medically qualified doctor (oversight in this instance is confirmation that the eligibility decision is correct, established by means of the GCP-trained doctor's signature on the trial prescription within a reasonable time scale following recruitment, as above).

(ii) Consent

Informed consent (which may or may not be accompanied by child assent, depending on the age and understanding of the child and at the discretion of the clinician and parent) will be obtained for all children by:

- (d) a GCP-trained GP or Nurse who has been trained in the trial procedures, OR;
- (e) a non GCP-trained healthcare professional (GP or Nurse) who has been trained in the trial procedures by a GCP-trained GP, and with oversight from a GCP-trained GP (oversight in this instance is: (1) written confirmation from a GCP-trained GP that the member of staff is sufficiently qualified and experienced to take consent, on behalf of the recruiting site, for this trial; and (2) countersignature on the consent form by the GCP-trained GP prior to the issue of the trial medication).

(iii) Issue of the trial medication

The trial medication may be issued to the parents of participating children, who have been recruited to one of the two ear drop arms, by a suitably qualified and GCP-trained GP, Nurse or other healthcare professional who has received training in the trial procedures.

Persons authorised to undertake the above activities on behalf of the recruiting site, will be documented on the trial delegation log.

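### The doctor's confirmation of a nurse's or ANP's eligibility decision rests on the trial prescription, which the glossary limits to the drop arms and Section 6.4 does not

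*Protocol*

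**What the plan says.** Section 6.11 allows nurses and ANPs to assess eligibility with oversight by a GCP-trained doctor, and defines that oversight as confirmation that the eligibility decision is correct.

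- For a nurse or other healthcare professional, it is "established by means of the GCP-trained doctor's signature on the trial prescription prior to the issue of the trial medication".
- For an ANP, it is "established by means of the GCP-trained doctor's signature on the trial prescription within a reasonable time scale following recruitment".
- Where a doctor is present at an ANP's site, "this oversight will take the form of GP/doctor authorisation of the completed trial prescriptions within a reasonable timescale following recruitment".
- For nurse-led sites: "This oversight will take the form of authorisation of the completed trial prescriptions by the CEDAR CI", or by a delegated GP.

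The glossary entry for Trial Prescription (Appendix 2) says: "The eligibility of a child to take part in the CEDAR trial must therefore be confirmed by a" qualified GP. This is not limited by arm. The entry then says: "The purpose of the trial prescription is to confirm the issue of the trial" medicine. The form also documents which medicine packs were issued and records eligibility judgements. It is completed as part of "the recruitment process for children recruited to one of the two active arms of" the RCT, which from the context means the two ear-drop arms.

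Section 6.4 (Entry into the RCT or OCS) describes a different sequence. Parents joining the RCT sign consent, "after which the Responsible Clinician will sign the Trial Prescription", and the parent is given the Patient Pack. Only the medicines depend on the arm. The same section says that a child later found ineligible is entered on a screening form, the rest of that child's data are destroyed, and a protocol deviation is recorded.

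Section 9.6 has the clinician open the Patient Pack after eligibility and consent, and opening it shows whether the child has drops. Section 12.5 analyses the primary comparison, active drops against no drops, by intention to treat.

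**The concern.** An eligibility confirmation should apply equally to every arm and be made before allocation is known, or without knowledge of it. Here the only defined vehicle for the doctor's confirmation is a form that documents the issue of drops. If the form exists only in the drop arms, a child recruited by a nurse or ANP gets a second, medical look at eligibility in those arms and not in the no-drops arm, and that look comes after the pack has been opened.

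This would be a governance gap only, were it not for the Section 6.4 rule on data. If a child found ineligible after randomisation loses the rest of their data, a check that runs in one arm of the primary comparison can remove children from that arm and not from the other. An intention-to-treat comparison is meant to prevent exactly that. Nurse-led recruitment is a real case: Section 9.5 names a nurse-led urgent care centre.

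**Working it through.** **Step 1. Which children have a prescription, and when?**

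| Source | Children covered | Timing |
|---|---|---|
| 6.11, nurse route | Not stated | Before the drops are issued |
| 6.11, ANP route and nurse-led sites | Not stated | A reasonable time after recruitment |
| Glossary | The two drop arms | Must follow opening of the pack, since it records the packs issued |
| 6.4 | Reads as all RCT entrants | After consent, listed before the pack is given |

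The last two rows cannot both hold. On the 6.4 reading, a form that documents issued packs is signed before anyone knows whether there is a pack to issue. On the glossary reading, the nurse-route timing has no meaning for a no-drops child, because no medicine is issued.

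**Step 2. What follows if the glossary governs?** A no-drops child recruited by a nurse or ANP has no document on which a doctor confirms eligibility, although the glossary requires confirmation for every child. In the drop arms the confirmation follows opening of the pack, and for ANPs it may follow issue of the drops. The GP countersignature in 6.11(ii) covers consent, so it does not fill the gap.

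**Step 3. Which comparisons are exposed?** Active and placebo children get the same check, so that comparison is unaffected. Comparisons with no drops, including the primary one, are exposed. The children without confirmation are at most the nurse- or ANP-recruited part of the no-drops arm, which is planned at 167 of 501 (3 × 167).

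**Step 4. How large could the effect be?** The protocol states no figure on this point, so there is none to reproduce. What follows is illustration on assumed inputs.

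*Shift in the active arm.* Assume 25–75% of children are recruited by non-doctors and 2–10% of those fail the check. The share r removed from the active arm then runs from 0.25 × 0.02 = 0.005 to 0.75 × 0.10 = 0.075. Assume also that all removed children would take antibiotics and that the active rate before removal is 70%. The rate falls by 0.70 − (0.70 − r)/(1 − r) = 0.30r/(1 − r):

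- r = 0.005: 0.15 percentage points
- r = 0.025: 0.77 points
- r = 0.075: 2.4 points

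*Effect on the test when there is no true difference.* Let p be the antibiotic rate among eligible children and e the ineligible share. All ineligible children take antibiotics, and they are removed from the drop arm only. The no-drops rate is (1 − e)p + e, the drop-arm rate is p, and the spurious difference is e(1 − p). With 133 evaluable per arm (Section 12.1) and standard error √(2p̄(1 − p̄)/133), where p̄ is the mean of the two rates, the two-sided 5% test rejects as follows:

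| e (children of 167) | Difference, p = 80% | Rejection rate | Difference, p = 60% | Rejection rate |
|---|---|---|---|---|
| 1% (about 2) | 0.2 points | 5.0% | 0.4 points | 5.1% |
| 2% (about 3) | 0.4 points | 5.1% | 0.8 points | 5.2% |
| 5% (about 8) | 1.0 points | 5.5% | 2.0 points | 6.3% |
| 10% (about 17) | 2.0 points | 7.0% | 4.0 points | 10.3% |

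For comparison, the trial is designed to detect a 20-point difference.

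**The case against.** Much of the case on the other side stands. Section 6.4 is body text and can be read as a prescription for every RCT child, signed before the pack is given. An earlier sentence of the glossary entry also ties authorisation of the prescription to eligibility, not to arm. If that reading is the intended one, the initial signature does not depend on arm or follow allocation. The finding is therefore a contradiction to be reconciled, and sites could follow either version.

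A reader might infer three stronger things, which the documents do not support.

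- *That no-drops children are never checked.* Sections 6.4, 9.1 and 9.6 have a trained recruiter complete the eligibility check before randomisation in every arm. Section 6.11 lets an ANP without a doctor on site seek a GP's advice on borderline cases. What may be missing is the doctor's confirmation.
- *That late ineligibility can surface in the drop arms only.* The site self-audits, the 10% quality checks and the for-cause checks in Section 14.2 are not limited by arm. They are self-checks, samples or triggered checks, however, and do not amount to a doctor's confirmation of each child.
- *That any bias must favour drops.* That holds only if removed children take antibiotics more often than the rest of the arm. It is plausible for children who needed same-day antibiotics. But nothing says that a doctor who signs later re-examines the child, and errors visible on paper, such as age or recent research participation, have no stated link to antibiotic use.

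It can also be said that nothing explicitly removes a child when a doctor declines to sign, and that the analysis is by intention to treat. The data rule in 6.4 weakens this. Its mention of a screening form might suggest children not yet entered, but it follows the definition of trial entry and calls for a protocol deviation. Appendix 10, by contrast, keeps the data already collected from withdrawn children.

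**Conclusion.** The concern holds as an internal contradiction with a route to bias. The glossary and Section 6.4 disagree on which children have the only form that carries the doctor's eligibility confirmation for nurse- and ANP-recruited children. If the glossary governs, that confirmation is absent in the no-drops arm and follows allocation in the drop arms. With the data rule in 6.4, ineligibility could then be found and acted on more systematically in the drop arms, to the detriment of the primary comparison.

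The size and direction of any bias cannot be derived from the protocol. It is probably small: on the assumed inputs, the rejection rate stays between 5.0% and 6.3% with up to 5% of the drop arm removed, and rises to 7.0–10.3% only at 10%. Those figures rest on every removed child being an antibiotic consumer and on no matching removals in the no-drops arm, both of which are assumptions. The point should be corrected because the remedy is cheap and protects the primary comparison.

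**What to change.** 1. Record the doctor's eligibility confirmation on the baseline eligibility form, for every RCT child whatever the arm. The recruiter signs that form before the Patient Pack is opened. Any later countersignature by a doctor is made on that form without sight of the allocation.
2. Keep the trial prescription only to document the issue of drops.
3. Reconcile Section 6.4, Section 6.11 (the numbered oversight items and part (i)) and the glossary entry accordingly.
4. Amend the data rule in Section 6.4 so that a randomised child later found ineligible stays in the intention-to-treat set, subject to consent, with a protocol deviation recorded. Step 1 alone would leave this route to exclusion open.

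The cost is wording in three places and one signature line on an existing form. The one downside is small: doctors also countersign forms for no-drops children. No extra visits or staff are needed.
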